7.1.3. Special populations

To date, only patients with adequate renal and hepatic function have been studied (see section 4.4 product data sheet).

Cetuximab has not been studied in patients with pre-existing haematological disorders (see section 4.4 product data sheet).

No dose adjustment is necessary in the elderly, although the experience in patients aged 75 years and over is limited.

7.1.4 Contraindications

Erbitux is contraindicated in patients with known severe (Grade 3 or 4) hypersensitivity reactions to cetuximab.

Before starting a combination treatment, the contraindications of the concomitantly used chemotherapy agents should be taken into account.

7.1.5. Warnings and precautions

Respiratory disorders

Individual cases of interstitial lung disease have been reported in which the causal relationship with cetuximab is unknown. If interstitial lung disease is diagnosed, cetuximab should be discontinued and the patient treated appropriately.

Skin reactions

If a patient develops a severe skin reaction (grade ≥ 3 ; US National Cancer Institute - Common Toxicity Criteria, NCI-CTC, v3.0), cetuximab treatment should be discontinued. Treatment can be resumed only if the reaction subsides to grade 2 (see section 4.8 of the product data sheet).

If the severe skin reaction has occurred for the first time, treatment can be resumed without change in dose.

If severe skin reactions occur for the second or third time, cetuximab should be stopped again. Treatment can be resumed at a lower dose (400 mg / m^2 after the second time, and 300 mg / m^2 after the third time) only if the reaction has subsided to grade 2.

If severe skin reactions appear for the fourth time, or they do not subside to grade 2 during treatment interruption, permanent discontinuation of cetuximab treatment is required.

Single-arm, multicenter, prospective phase II clinical trial for biomarker validation in patients with advanced and / or metastatic colorectal cancer with non-mutated KRAS gene treated with chemotherapy plus biweekly cetuximab as first-line therapy

Electrolyte disturbances

Progressive decreases in serum magnesium levels occur frequently, which can lead to severe hypomagnesemia. Hypomagnesemia is reversible after stopping cetuximab treatment. In addition, hypokalemia may occur as a result of diarrhea.

Hypocalcemia can also occur; in particular the frequency of severe hypocalcaemia may be increased when used in combination with platinum-based chemotherapy.

Serum electrolyte level determinations should be performed prior to treatment and periodically during treatment with cetuximab. Electrolyte replenishment is recommended as needed.

Neutropenia and related infectious complications

Patients receiving cetuximab in combination with platinum-based chemotherapy are at increased risk of severe neutropenia, which can lead to later infectious complications such as febrile neutropenia, pneumonia, or sepsis. Close monitoring is recommended in these patients, especially in those with skin lesions, mucositis or diarrhea, which may facilitate the development of infections (see section 4.8 of the product data sheet).

Special populations

To date, only patients with adequate kidney and liver function (serum creatinine \leq 1.5 times, transaminases \leq 5 times and bilirubin \leq 1.5 times the upper limit of normal) have been studied.

Cetuximab has not been studied in patients with one or more of the following laboratory parameters:

- *hemoglobin <9 g / dl*
- *white blood cell count <3000 / mm³*
- *absolute neutrophil count <1500 / mm³*
- *platelet count <100,000 / mm³*

7.1.6. Interaction with other medicinal products and other forms of interaction

The frequency of severe leukopenia or severe neutropenia may be higher and therefore may lead to a higher rate of infectious complications such as febrile neutropenia, pneumonia, and sepsis with combination with platinum-based chemotherapy, compared to chemotherapy based on platinum alone (see section 4.4 of the product data sheet).

The frequency of cardiac ischemia, including myocardial infarction and congestive heart failure, and the frequency of hand-foot syndrome (palmoplantar erythrodysesthesia) were higher with the combination with 5-fluorouracil than with the infusion of 5-fluorouracil alone.

A formal interaction study showed that the pharmacokinetics of cetuximab remain unchanged after co-administration of a single dose of irinotecan (350 mg / m² body surface area). Also, co-administration of cetuximab did not alter the pharmacokinetics of irinotecan.

No other formal interaction studies with cetuximab have been performed in humans.

7.1.7. Pregnancy and breastfeeding

EGFR is involved in the development of the fetus. Limited observations in animals indicate a

placental transfer of cetuximab and other IgG1 antibodies have been shown to cross the placental barrier. Animal data did not reveal indicative evidence of teratogenicity. However, depending on the dose, a higher incidence of abortions was observed (see section 5.3). There are insufficient data in pregnant or lactating women.

It is strongly recommended that cetuximab be administered during pregnancy or in women not using adequate contraception only if the potential benefit to the mother justifies the potential risk to the fetus.

It is recommended that women do not breastfeed their infants during treatment with cetuximab and for 2 months after the last dose, as it is unknown whether cetuximab is excreted in human milk.

7.1.8. Adverse Reactions

See SmPC of the product.

7.1.9. Overdose

Currently there is limited experience with single doses greater than 400 mg / m² of surface area. body or weekly administrations of doses greater than 250 mg / m² of body surface. In clinical trials with doses up to 700 mg / m² administered every 2 weeks, the safety profile was consistent with that described in section 4.8. of the product data sheet.

7.1.10. Pharmaceutical Data

List of excipients

Sodium chloride

Wisteria

Polysorbate 80

Citric acid monohydrate

Sodium hydroxide

Water for injections

Incompatibilities

This medicinal product must not be mixed with others except those mentioned in section 6.6 of the product's technical data sheet. A separate infusion line must be used.

Period of validity

2 years.

The physical and chemical stability of cetuximab 5 mg / ml has been demonstrated during use for 48 hours at 25 ° C, if the solution is prepared as described in section 6.6 of the product data sheet.

Cetuximab does not contain any antimicrobial preservatives or bacteriostatic agents. From the point of view of a microbiological point of view, the drug should be used immediately after opening. But used immediately, storage times and conditions prior to use are

responsibility of the user and normally they should not exceed 24 hours at a temperature between 2 and 8°C, unless the opening has taken place under controlled and validated aseptic conditions.

Special precautions for storage

Single-arm, multicenter, prospective phase II clinical trial for biomarker validation in patients with advanced and / or metastatic colorectal cancer with non-mutated KRAS gene treated with chemotherapy plus biweekly cetuximab as first-line therapy

Store in a refrigerator (2 ° C to 8 ° C). Do not freeze.
For storage conditions after opening, see section "Shelf life"

7.1.11. Cetuximab dose modifications for infusion-related reactions

If an infusion-related reaction occurs, the investigator should institute therapeutic measures corresponding to the best available medical practice. Based on previous experience with infusion-related reactions

Re-administration of treatment after an infusion-related reaction

Once the infusion rate of cetuximab has been decreased due to the occurrence of an infusion-related reaction, this decrease will continue during subsequent infusions. If a subject develops a second infusion-related reaction at the slower infusion rate, cetuximab should be permanently discontinued. If at any time a patient experiences a Grade 3 or 4 infusion-related reaction, cetuximab will be withdrawn from treatment. If there is any doubt as to whether a subject's reaction is a grade 1-4 infusion-related reaction, the study coordinator and / or principal investigator should be contacted immediately to discuss and grade.

Proposal to synchronize cetuximab and chemotherapy in case of delays

| | Week 1 | Week 2 | Week 3 | Week 4 | Week 5 | Week 6 | Week 7 | Week 8 | Week 9 | Week 10 | Week 11 | Week 12 |
|--------------------------------|--|--------|--------|--------|--------|--------|---|--------|--------|---------|---------|---------|
| Cetuximab (mg/m ²) | 500 | -- | 500 | -- | 250 | 250 | 500 | -- | 500 | 250 | 500 | -- |
| Chemotherapy | dose | -- | dose | -- | dose | dose | dose | -- | dose | -- | dose | -- |
| | Toxicity requiring delay in chemotherapy | | | | | | Cutaneous toxicity requiring delay in cetuximab | | | | | |

Whenever chemotherapy is administered, cetuximab will be administered at a dose of 500 mg / m² unless dermal toxicity precludes administration.

Whenever chemotherapy must be delayed, cetuximab will be administered at a dose of 250 mg / m² in order to allow the administration of 500 mg / m² one week later, coinciding with the planned administration of chemotherapy.

Provided that cetuximab has been delayed due to skin toxicity, but chemotherapy is given as planned, resolution of skin toxicity will be verified one week later. If appropriate, cetuximab will be administered at a dose of 250 mg / m² to allow a return to synchronous administration at the time of the next chemotherapy administration. It is recommended to use these same principles in anticipated cases of dose reduction of cetuximab.

Cetuximab dose reduction in case of skin reactions:

Other reasons to discontinue cetuximab;

If a patient develops breakthrough illness that, in the opinion of the investigator, requires discontinuation of cetuximab treatment, it should be resolved within a framework that does not require delaying more than one infusion.

After stopping treatment, the patient will continue with cetuximab at the dose she was receiving before treatment.

If treatment must be delayed for a longer period, the patient will discontinue treatment. In special cases with the approval of the coordinator the patient could continue with the treatment.

Treatment with cetuximab will not be interrupted due to delays due to chemotherapy toxicity. In case of chemo delays, the patient will receive cetuximab treatment as planned.

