7.1.1. Dosage

Before the first infusion, the patient should be administered an antihistamine and a corticosteroid.

This premedication is recommended for all subsequent infusions.

Cetuximab will be administered every 2 weeks, the dose is 500 mg / m².

In reference to the dosage or modifications of the recommended dose of concomitantly used chemotherapeutic agents, consult the SmPC of these drugs. They should not be administered until one hour after the end of the cetuximab infusion.

Biweekly cetuximab treatment should be continued until underlying disease progresses.

Once a dose reduction has been made, a dose escalation will not be allowed in subsequent cycles.

In no case can the patient be kept in the study with Oxaliplatin or Irinotecan in monotherapy, or in combination with cetuximab without 5-FU.

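### Protocol section 7.1.11 calls for cetuximab 500 mg/m² with every chemotherapy dose, without qualification for patients whom section 7.1.5 reduces to 400 or 300 mg/m² and section 7.1.1 bars from escalation

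*Protocol*

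**What the plan says.** Three parts of the protocol govern the cetuximab dose after skin toxicity.

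- **Section 7.1.5 (skin reactions).** A reaction of grade 3 or higher stops cetuximab, which may restart only if the reaction falls to grade 2. For the first event: "If the severe skin reaction has occurred for the first time, treatment can be resumed without change in dose". For the second and third: "Treatment can be resumed at a lower dose", with the levels given as "400 mg / m^2 after the second time, and 300 mg / m^2 after the third time". A fourth event, or failure to fall to grade 2, ends cetuximab permanently.
- **Section 7.1.1 (dosage).** "Once a dose reduction has been made, a dose escalation will not be allowed in subsequent cycles".
- **Section 7.1.11 (synchronising cetuximab and chemotherapy after delays).** "Whenever chemotherapy is administered, cetuximab will be administered at a dose of 500 mg / m² unless dermal toxicity precludes administration". Where cetuximab was held for skin toxicity but chemotherapy went ahead, "resolution of skin toxicity will be verified one week later". The text continues: "If appropriate, cetuximab will be administered at a dose of 250 mg / m² to allow a return to synchronous administration". For a chemotherapy delay it uses the same fixed figure: "Whenever chemotherapy must be delayed, cetuximab will be administered at a dose of 250 mg / m² in order to allow" a 500 mg/m² dose one week later. The block ends by recommending that its principles also be used where a reduction of cetuximab is anticipated. It gives no reduced-dose figures and does not refer to sections 7.1.1 or 7.1.5.

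**The concern.** The sentence on the chemotherapy-day dose has one exception, skin toxicity that prevents dosing. That covers a patient from whom cetuximab is being withheld. It does not plainly cover a patient who has recovered enough to be treated but has already been moved to a lower level. For that patient, section 7.1.11 states one dose and sections 7.1.1 and 7.1.5 state another.

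The patients affected have had at least two severe skin reactions, so a wrong reading bears on safety. About 30 centres were planned (section 5.2), and nothing says which section takes precedence, so two centres could treat the same patient differently and each cite the protocol. Describing the safety profile of 500 mg/m² every 2 weeks is a secondary objective (section 4.6.2). The SAP's protocol-deviation table (Table 5) has a category for incorrect dosing regimen. Under conflicting rules, one and the same dose is compliant by one section and a deviation by another.

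**Working it through.** The plan states no figure to reproduce. The check sets the sections side by side and then takes dose ratios.

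**Inputs.** Reduced levels of 400 and 300 mg/m² (section 7.1.5); no escalation after a reduction (section 7.1.1); 500 mg/m² with chemotherapy and a 250 mg/m² catch-up (section 7.1.11).

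**Step 1: do the sections apply to the same patient?** Take a patient whose second severe reaction has fallen to grade 2, with chemotherapy due. Section 7.1.5 permits a restart, so skin toxicity no longer prevents dosing. This is my reading, since the protocol does not define when toxicity precludes administration. Section 7.1.5 then gives 400 mg/m², and section 7.1.11 gives 500 mg/m². After a third reaction the pair is 300 and 500.

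**Step 2: later cycles.** Section 7.1.1 keeps the patient at or below the reduced level. Its sentence names no drug, but it stands in the cetuximab dosage section directly after a sentence on cetuximab. Section 7.1.11 gives 500 mg/m² at each chemotherapy administration. If the no-escalation sentence were held not to cover cetuximab, the conflict between sections 7.1.5 and 7.1.11 at restart would remain.

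**Step 3: size of the conflict.**

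| Level under 7.1.5 | Dose under 7.1.11 | Excess |
|---|---|---|
| 400 mg/m² | 500 mg/m² | (500 − 400) / 400 = 25% |
| 300 mg/m² | 500 mg/m² | (500 − 300) / 300 = 67% |

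**Step 4: does section 7.1.11 resolve it?** Its closing recommendation can be read in two ways. Either the schedule is scaled to the reduced level, or the 500 and 250 mg/m² figures are applied unchanged. Under the first reading each site must work out its own figures. Under the second, the excesses in step 3 follow. The text does not choose between them.

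**Step 5: secondary ambiguity.** Take a first severe reaction that is at grade 2 one week later. Section 7.1.5 allows a restart with no change in dose. Section 7.1.11 looks for resolution, with no grade attached, and then offers 250 mg/m² where appropriate, which is 250 / 500 = 50% of the full dose. The recovery criterion and the dose at restart are both worded differently.

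**The case against.** The best defence is that section 7.1.11 is not a dose-reduction rule at all. The block is headed as a proposal and explains timing through an example schedule that starts at 500 mg/m². The skin-reaction rule is in section 7.1.5, the ban on escalation in section 7.1.1 is categorical, and no passage authorises re-escalation. Elsewhere in section 7.1.11, a patient who interrupts cetuximab for an intercurrent illness goes back to the dose held before. The closing recommendation can naturally be read as scaling the schedule to the reduced level. A heading on cetuximab dose reduction for skin reactions follows it with no text beneath. That text may have been lost in reading the file, so the empty heading is not counted here as an omission.

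Much of this stands. It shows that the conflict is one of wording and that re-escalation was probably not intended. It does not remove the conflict: under the proposal heading the wording is mandatory, the recommendation carries no figures, and there is no cross-reference or order of precedence. The intercurrent-illness rule shows that the protocol could tie a dose to the patient's own level, and the chemotherapy-day sentence does not do so.

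The defence is stronger on the secondary ambiguity. Both sections are permissive there, 250 mg/m² can be read as a one-off bridge that leaves the dose level unchanged, and resolution can be read together with grade 2.

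Three stronger readings are tempting, but the documents do not support them.

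- A reader might add the catch-up to the next chemotherapy-day dose, 250 + 500 = 750 mg/m² about a week apart, and set that against a single 300 mg/m² dose. The 250 belongs to the delayed cycle and the 500 to the next, so the like-for-like totals are 2 × 300 = 600 (750 / 600 = 1.25) and 2 × 400 = 800 (750 / 800 = 0.94). Moreover, a patient at 300 mg/m² who has a fourth severe reaction stops cetuximab for good. The sequence could arise only with a non-severe skin delay or within the third reaction's own delay.
- A reader might conclude that section 7.1.11 recognises only two cetuximab doses. The empty heading makes that unsafe.
- A reader might infer harm to the PFS analysis. SAP section 6.5.1.3 leaves patients with significant deviations out of the efficacy analysis, but dosing level is not among its examples, and nothing shows that any patient was excluded for this reason.

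**Conclusion.** The concern holds as an internal contradiction. Read literally, section 7.1.11 gives a patient on a reduced dose 25% or 67% more cetuximab per chemotherapy-day administration than sections 7.1.1 and 7.1.5 allow. The wording of skin recovery and of the restart after a first reaction is a lesser ambiguity.

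The conclusion rests on two assumptions: that a patient allowed to restart at grade 2 is no longer someone in whom skin toxicity precludes dosing, and that the no-escalation sentence covers cetuximab. It does not rest on the empty heading.

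The number of patients affected cannot be estimated. The documents give no rate of repeated severe skin reactions. The 11.4% grade 3 and 4 acne-like rash in section 4.3 comes from a different cohort of 70 patients given irinotecan plus cetuximab, and does not separate first from repeated events. Sample size, power and the primary analysis are not called into question. The point matters because it concerns dosing after severe toxicity.

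**What to change.** The sponsor must reconcile sections 7.1.1, 7.1.5 and 7.1.11 so that one consistent instruction applies to patients whose cetuximab was reduced or delayed for skin toxicity, including how skin recovery is judged. Which dose or rule is right is a clinical decision, and none is proposed here. The sponsor should also check whether text is missing beneath the empty heading in section 7.1.11.

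The SAP gives study completion as June 2017. For data already collected, the useful step is therefore to document which section sites followed, to apply that consistently when classifying dosing deviations, and to state it when cetuximab safety is reported.

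The cost is a wording change in the cetuximab sections and a note to sites if the protocol is still in use or is reused, plus a review of dosing records for patients with repeated severe skin reactions. Design, sample size and planned data collection do not change.

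### The protocol gives three inconsistent cetuximab instructions for a chemotherapy delay, and no text says which one governs

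*Protocol*

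**What the plan says.** The base plan is in Protocol 7.1.1: "Cetuximab will be administered every 2 weeks, the dose is 500 mg / m²". Four further statements bear on what happens when chemotherapy is late.

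- **Protocol 7.1.11, synchronisation text**, under the line "Proposal to synchronize cetuximab and chemotherapy in case of delays": "Whenever chemotherapy must be delayed, cetuximab will be administered at a dose of 250 mg / m²". The stated purpose is to let 500 mg/m² be given one week later with chemotherapy. The sentence before it reads "Whenever chemotherapy is administered, cetuximab will be administered at a dose of 500 mg / m² unless dermal toxicity precludes administration".
- **Protocol 7.1.11, closing sentences**, after the line on other reasons to discontinue cetuximab: "Treatment with cetuximab will not be interrupted due to delays due to chemotherapy toxicity". Then: "In case of chemo delays, the patient will receive cetuximab treatment as planned".
- **Protocol 8.3** gives cetuximab 500 mg/m² on day 1 of each cycle. It defines a cycle as 14 ± 3 days, extended for as long as chemotherapy toxicity takes to clear.
- **Protocol 7.1.1** adds a general bar: "Once a dose reduction has been made, a dose escalation will not be allowed in subsequent cycles".

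Delays are expected: Protocol 7.2.2 and 7.3.2 allow a new chemotherapy cycle to start up to 4 weeks late. The schedule footnotes in SAP section 6 say only that cycles may be delayed for toxicity of either component.

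**The concern.** The synchronisation text, the closing sentences of 7.1.11 and section 8.3 all govern the same event. The first names a 250 mg/m² dose. The second keeps cetuximab going as planned, and the only two-weekly plan stated is 500 mg/m² in 7.1.1. The third, taken literally, makes cetuximab wait with chemotherapy. A site could follow any of them and believe it was following the protocol.

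Two things are at stake.

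- **Safety.** A secondary objective (Protocol 4.6.2, SAP 5.2) is to describe the safety of 500 mg/m² every 2 weeks. If practice during delays differs between sites, the regimen being described is not uniform.
- **Deviations.** SAP Table 5 has a row for incorrect dosing regimen, and SAP 6.5.1.3 removes patients with significant protocol deviations from the efficacy analysis. Without a single rule, nobody can say whether a given infusion during a delay was a deviation. SAP Table 7 would not reveal the difference, because it counts cycles received, not dose.

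**Working it through.** The plan gives no figure to reproduce, so the check applies each text to the same case.

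**One-week delay.** Chemotherapy is due in week 5 and given in week 6.

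- *A, synchronisation text:* 250 in week 5, 500 in week 6. Total 250 + 500 = 750 mg/m².
- *B, closing sentences read plainly:* the planned 500 in week 5. Chemotherapy is then given in week 6, and 7.1.11 requires 500 mg/m² whenever chemotherapy is given. Total 500 + 500 = 1000 mg/m², with the doses one week apart. If cetuximab instead keeps its own two-weekly clock, week 6 has chemotherapy without cetuximab, which breaks that same sentence.
- *C, section 8.3:* day 1 of the new cycle moves to week 6. Total 500 mg/m², with nothing in week 5, against the statement that cetuximab is not interrupted for chemotherapy delays.

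**Two-week delay.** Chemotherapy moves from week 5 to week 7. The text describes only a one-week gap, so A needs the assumption that the 250 mg/m² dose repeats weekly.

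- *A:* 250 + 250 during the delay = 500, then 500 with chemotherapy. Total 1000 mg/m².
- *B:* 500 during the delay, then 500 with chemotherapy. Total 1000 mg/m².
- *C:* nothing during the delay, then 500 mg/m².

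**Four-week delay**, same assumption: A gives 4 × 250 = 1000 mg/m² during the delay and B gives 2 × 500 = 1000 mg/m².

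So A and B differ by 1000 − 750 = 250 mg/m² in total for a one-week delay and do not differ in total for a two- or four-week delay. At the first infusion of the delay they always differ, 250 against 500 mg/m². C differs from both in every case.

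**The one-week case against the protocol's own text.** Protocol 7.1.9 describes experience with weekly doses above 250 mg/m² as limited. It also reports a consistent safety profile for doses up to 700 mg/m² every 2 weeks. Reading B puts two 500 mg/m² doses one week apart, a pattern that the protocol neither endorses nor rules out.

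**The case against.** The strongest reply is that the closing sentences of 7.1.11 are about whether cetuximab continues, not how much is given. The synchronisation scheme has just been set out in the same section, so the plan referred to may be that scheme. The reading is possible and makes this an ambiguity at least as much as a contradiction. But the text does not say so. Earlier in 7.1.11 the same phrase describes chemotherapy that keeps its original schedule, and the scheme itself is headed a proposal. Nor does the reply deal with section 8.3.

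Four stronger inferences are tempting, and the documents do not support them.

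- **That the synchronisation table is wrong.** As it reads here, it shows 250 mg/m² beside a chemotherapy dose in weeks 5 and 6, under a label of delayed chemotherapy. Marking of withheld doses may have been lost in text extraction. On that assumption, 250, 250, 500 fits the synchronisation text for a two-week delay, because week 7 is one week after the last 250 mg/m² dose. The table shows no established error.
- **That exposure differs two-fold.** 500/250 = 2 holds per infusion only. The 250 mg/m² dose covers one week and the 500 mg/m² dose two, so totals can be equal.
- **That the bar on escalation forbids returning from 250 to 500.** The synchronisation text expressly provides for that return. The reduction levels for skin reactions in 7.1.5 are 400 and 300 mg/m², not 250. What remains is that no sentence says whether 250 mg/m² counts as a reduction.
- **That the efficacy analysis is compromised.** The examples of significant deviations in SAP 6.5.1.3 are RAS mutations, missing biomarker data and not receiving cetuximab. A dose given during a delay is not among them.

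**Conclusion.** The point holds as an internal inconsistency of moderate severity. For a one-week delay the texts can yield 750, 1000 or 500 mg/m². The disagreement concerns the individual dose and its timing; cumulative dose under the two parts of 7.1.11 can be the same over a two-week delay.

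This rests on two assumptions: that the closing sentences of 7.1.11 carry their plain meaning, and, for delays beyond one week, that the 250 mg/m² dose repeats weekly. If the sponsor meant the closing sentences to point to the synchronisation scheme, that part of the conflict disappears and the conflict with section 8.3 remains.

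The consequence falls on the safety description and on the classification of dosing deviations. The primary endpoint definition, the 115-event target and the power are unaffected.

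**What to change.** Reconcile the two parts of Protocol 7.1.11 and section 8.3 into one rule for a chemotherapy delay. It should state the cetuximab dose and timing during the delay, what happens when the delay exceeds one week (up to the 4 weeks allowed), and what is given when chemotherapy resumes. State whether the 250 mg/m² synchronisation dose counts as a dose reduction under 7.1.1. Check the synchronisation table against the original document so that it illustrates the same rule. The choice of rule belongs to the sponsor and investigators; this review does not make it.

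The cost is amendment wording, with the ethics committee approval that Protocol 11.3.1 requires.

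The SAP gives a completion date of June 2017. For data already collected, the practical step is to tabulate, by site, the cetuximab doses given during chemotherapy delays, and to state which rule was used to classify dosing deviations. Protocol 12.1 has the amount used recorded in the drug administration log, so this should need tabulation only.
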